4.1 Primary endpoint

The primary outcome will be self-reported daily average numerical pain intensity during the past 24 hours. The comparisons are following as following: 1) primary comparison: arm A vs. arm B; 2) secondary comparison: arm A vs. arm C; exploratory comparison: arm B vs. arm C. Since the three comparisons have different levels of importance, no correction will be done for multiple comparisons.

4.1.1 Primary analysis

The primary analysis will be the comparison of self-reported pain intensity between arm A and arm B. An intent-to-treat analysis will be performed on data from participants who complete baseline. Data transformation (e.g., log10, square root) may be performed to improve distribution normality as appropriate. Response profiles analysis will be performed if the trend of pain intensity over time is not linear. We will compare different covariance pattern models (e.g., unstructured, compound symmetry) based on AIC and identify a covariance model with the best fit to our data. This is a randomized controlled trial so that we can remove main group effect with assumptions about equal mean responses (i.e., pain scores) at baseline for the three treatment arms. Weekly or biweekly average of pain intensity from the daily diary will be calculated as a primary outcome. Time will be treated as a factor with 6 levels (i.e., baseline, weeks 1, 3, 5, 7, 8), and the mean response profiles will be compared between the arms. The treatment effect over time will be assessed by the significance of the treatment arm x time interaction using Wald test. Also, average change at the treatment period (weeks 5-8) from baseline will be compared between the groups. (Aim 1)

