Dronabinol and Vaporized Cannabis in Chronic Low Back Pain

Statistical analysis plan

Principal investigators:

**[name].
[name]. (retired)**

Protocol Statisticians:

**[name].
[name].**

April 24, 2020

1. Summary of Study Design

This study is a prospective, randomized, placebo controlled, double blind, phase 2/3 clinical trial of dronabinol and vaporized cannabis for the treatment of chronic low back pain. A total of 120 (n = 120) subjects with chronic low back pain, aged between 19-70 years will be randomized in a ratio of 1:1:1 to the three treatment arms (40 participants per arm): 1) vaporized 3.7% Δ9-THC /5.6% cannabidiol plus placebo oral pills, 2) oral Δ9-THC (dronabinol) plus vaporized placebo, and 3) double placebo. The three arms are shortly called 1) vaporized cannabis; 2) dronabinol; 3) placebo. After randomization, each patient will receive study medication at home for 8 weeks after which they will be tapered off of investigational treatments over two weeks. The three study periods include: i) Titration (weeks 0-4); ii) Treatment (weeks 5-8); iii) Tapering (Weeks 9-10). During the titration period, patients will undergo titration of vaporized medication from 4 puffs to 18 puffs, or oral medication from 5 mg qd to 10 mg tid per day. Subjects will be dropped from the study by the end of Week 4 if they are unable to tolerate the minimum amounts of medication described above, and replaced by another volunteer. During the treatment period, subjects will be expected to consume the amount of study medication that they titrated themselves up to by the end of week 4. During the tapering period, patients will slowly withdraw from medication over two weeks. During treatment at home (weeks 1-8), patients will maintain a paper daily diary to record their intake of study medications, and breakthrough pain medications, as well as pain relief measurements. Outcome measure (such as self-report forms and neuropsychological testing) will be collected during the six study visits. If participating in Driving Simulation, subjects with driver licenses will be scheduled for two experimental visits.

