5.1 Power Estimation

Power estimates for each outcome assumed a 5% significance level. Totally, N=120 subjects will be randomized in 1:1:1 ratio to the three treatment arms, that is, 40 subjects to each arm. Using the same 16% drop-out rate experienced in our previous study and that 87% of the completers possess a valid driver's license, a national average published by the Department of Transportation, power was calculated for 33 subjects per treatment arm (total N=99) for Aims 1 and 2, and 29 subjects per treatment arm (total N=87) for Aim 3. We have 80% power to detect effect sizes equivalent to Cohen's $d=0.54$ and $d=0.58$ for sample sizes 33 and 29 respectively. This effect size is based on differences between groups of changes from baseline at the end of the study (week 8). The power is calculated using specific formulas for a time-by-treatment interaction in a longitudinal linear mixed-effects model {Diggle PJ, Heagerty P, Liang KY, Zeger SL: Analysis of Longitudinal Data, 2nd edition, 2002, Oxford University Press, Oxford, p.29}. Power is expected to be higher for larger effect sizes and fewer dropouts.

6. Data and Safety Monitoring Committee (DSMC)

Progress reports will be presented to the DSMC every 6 months. Two reports (open and closed reports) will be generated and presented in two sessions.

Key study personnel and all DSMC members will attend the open session; *the open report* will present data in aggregate form (not by arm). Open session attendees will review presented summarized data for data completeness and accuracy (e.g., review ranges for numeric variables to catch any outliers/unusual observations).

The closed session will include only the study statistician and members of the DSMC; *the closed report* will present data by treatment arm, but in blinded fashion,

i.e., arms will be presented as arm X, arm Y, arm Z. Treatment labels can be revealed to the DSMC members upon their request if major concerns arise. Statistical comparison of relevant characteristics between the arms will be done. No interim analysis comparing primary outcomes between the arms will be performed in order to preserve the power of the primary analysis and the overall Type I error at 0.05 level till the end of the study, unless requested by the DSMC. Members of the DSMC will be asked to maintain confidentiality related to the interim data presented in the closed report until the end of the trial.

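### SAP 4.1.1 does not fix which test decides the primary A versus B comparison; the effect on type I error ranges from none to about 8.7%, depending on how the choice is made

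*SAP*

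**What the plan says.** SAP 4.1.1 contains three statements about the form of the primary analysis.

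- A condition: "Response profiles analysis will be performed if the trend of pain intensity over time is not linear". The SAP gives no linearity test, no threshold, no statement of whether the trend is judged pooled or by arm, and no model for the case where the trend is linear.
- A specification without a condition: "Time will be treated as a factor with 6 levels (i.e., baseline, weeks 1, 3, 5, 7, 8", with the treatment effect judged by a Wald test of arm by time.
- A further comparison, also without a condition: average change from baseline over weeks 5-8 between the groups.

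No sentence ranks the last two. SAP 5.1 bases power on "specific formulas for a time-by-treatment interaction in a longitudinal linear mixed-effects model" and states: "We have 80% power to detect effect sizes equivalent to Cohen's $d=0.54$ and $d=0.58$ for sample sizes 33 and 29 respectively". It adds: "This effect size is based on differences between groups of changes from baseline at the end of the study (week 8". The level is given as "Power estimates for each outcome assumed a 5% significance level", and SAP section 6 gives preserving the "overall Type I error at 0.05 level till the end of the study" as a reason for having no interim efficacy analysis.

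**The concern.** A condition on linearity implies that something else is done when the trend looks linear. The obvious candidate is a model with time as a straight line, where arm by time is one slope difference (1 df) rather than five contrasts (5 df). On that reading the outcome data choose the test. Even without it, the paragraph names two tests of A versus B and leaves open which one decides.

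Two things are at stake. First, if the choice is correlated with the A-B difference, the 5% level is not kept. Second, the tests answer different questions and often disagree, so two analysts who both follow 4.1.1 could report different primary results from the same data.

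The condition also serves little purpose. SAP section 1 has dose rising through week 4, after which "subjects will be expected to consume the amount of study medication that they titrated themselves up to by the end of week 4". That gives no reason to expect a straight line over weeks 0-8.

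**Working it through.** **1. The plan's own power figure.** Inputs from SAP 4.1.1 and 5.1: 33 or 29 per arm, d=0.54 or 0.58 as the difference in change at week 8, and times 0, 1, 3, 5, 7, 8. Assumed: two-sided 5%, and a within-subject correlation ρ, which the SAP does not state.

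- A plain two-sample comparison does not reproduce 80%: Φ(0.54·√(33/2) − 1.96) = 59.2%, and 59.8% for d=0.58 with n=29.
- The slope-difference formula does: n = 2(z₀.₉₇₅ + z₀.₈₀)²(1−ρ) / [Sxx·(d/8)²]. The mean time is 4, so Sxx = 16+9+1+1+9+16 = 52. With ρ=0.5, n = 7.849 / (52 × 0.0675²) = 33.1 for d=0.54, and 28.7 for d=0.58. Power is 79.8% at n=33 and 80.4% at n=29.
- The match depends on ρ: 0.4 gives 72-73%, and 0.6 gives 88%.

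The stated power therefore fits a 1-df linear slope test. It does not describe the 5-df test.

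**2. Type I error of the possible choices.** Setting: A versus B, covariance treated as known (so small-sample effects are excluded), baseline means constrained equal as in 4.1.1, and each test alone at 5.0%. The linear fallback is an assumption. Simulations used at least 400,000 draws and several compound-symmetry and autoregressive correlations.

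| How the test is chosen | Type I error |
|---|---|
| One test fixed in advance | 5.0% |
| Slope or profile, linearity judged on the trend pooled over arms | 5.0% |
| Same, quadratic check on the A-B difference | 6.1-6.2% |
| Same, judged arm by arm or jointly | 6.6-7.1%, falling to 5% if the common trend is clearly curved |
| Same, full 4-df check on the A-B difference | 7.7-8.3% |
| Better of slope and profile tests | 8.5-8.7% |
| Better of the two tests named in 4.1.1 (5-df interaction, weeks 5-8 average) | 8.6-8.7% |

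Three rows can be checked by hand.

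- *Pooled check.* With equal arms the pooled trend is independent of the A-B difference. If p is the probability of switching, the size is p × 0.05 + (1−p) × 0.05 = 0.05.
- *4-df check on A-B.* Under the null the 5-df statistic splits into Z² (slope, 1 df) plus an independent Q (non-linearity, 4 df). The switch occurs if Q > 9.49, and the 5-df test rejects if Z²+Q > 11.07. Size = 0.95 × 0.05 + P(Q > 11.07) + P(9.49 < Q < 11.07 and Z²+Q > 11.07) = 0.0475 + 0.0258 + 0.0095 = 8.3%.
- *Either named test.* The same split, with Z now the weeks 5-8 contrast, gives P(Z² > 3.84 or Z²+Q > 11.07) = 8.6%.

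**3. Does the choice matter under a real effect?** Assume an effect that builds and then holds (0.25, 0.75, 1, 1, 1 at weeks 1, 3, 5, 7, 8), scaled to 80% power for the weeks 5-8 average. The slope test has 75-81% power and the 5-df test 61-64%. They disagree in 23-24% of trials.

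**4. Power if one test is fixed.** Assume a linear effect reaching d=0.54 at week 8, n=33 and ρ=0.5. The weeks 5-8 effect, averaged over the levels 5, 7 and 8, is 0.54 × (20/3)/8 = 0.45. Its variance factor is (0.75 + 2×0.25)/3 = 0.417 with baseline means constrained equal, so SE = √(0.417 × 2/33) = 0.159 and power = Φ(0.45/0.159 − 1.96) = 80.8%.

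| Test | Baseline free | Baseline constrained equal |
|---|---|---|
| Slope, 1 df | 79.8% | 88.2% |
| Weeks 5-8 average, 1 df | 61.0% | 80.8% |
| Arm by time, 5 df | 55.3% | 67.1% |

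**The case against.** The best defence is that the paragraph can be read as unconditional. Six-level time and the Wald test carry no qualifier, SAP 4.2.1 summarises the same strategy as an arm by six-visit test, and no linear-time model is written as an analysis anywhere in 4.1 or 4.2.1. The power formula is a planning tool and does not instruct the analyst. This stands in part: the linear fallback is inferred. But if the later sentences are unconditional, the conditional sentence contradicts them, and the reader still cannot tell whether the interaction or the weeks 5-8 average decides.

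A reader might infer that the trial's primary test has a true error rate of about 8% because the model is picked from the data. The documents do not support that. The sentence refers to the trend of pain, not to the trend in the A-B difference, and a pooled check is a natural reading that leaves the error at 5.0%. The held dose after week 4 also suggests curvature would usually be found, and then a pooled or arm-by-arm check leads to response profiles with little or no inflation.

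The disagreement figures rest on an assumed effect shape and assumed correlations. Because they arise under a real effect, they say nothing about type I error.

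**Conclusion.** The point holds as a failure to fix the deciding A versus B test, not as a demonstrated 8% error rate. The conditional sentence has no rule and no fallback, it conflicts with the unconditional text after it, and two named tests are left unranked.

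The firmest figure is the 8.6-8.7% for taking the better of the two tests that the SAP names, since it needs no assumed linear model. It is the cost if the better result is used; the SAP does not say that it will be. All these figures assume a known covariance and a two-sided 5% level. The match of the stated power to a slope test further assumes ρ=0.5.

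**What to change.** In SAP 4.1.1, before unblinding:

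- Delete the linearity condition, and state that time is always the six-level factor in the primary model.
- State that the A versus B decision rests on one contrast in that model, whatever shape is observed. The weeks 5-8 average change from baseline is already in the SAP and is a natural candidate. Say which time levels enter it and with what weights.
- List the 5-df arm by time test and any linear-trend model as supportive.

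In SAP 5.1, recompute and restate the power for the chosen contrast, giving the assumed within-subject correlation and how baseline is handled.

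The cost is a few sentences and one calculation, with no extra patients or data. The small downside is that the restated power may be less favourable. Under the assumptions in step 4 of the working, the weeks 5-8 average has 80.8% power with baseline means constrained equal but 61.0% without, and giving up the slope test loses power if the effect really is linear.

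### The primary arm-by-time Wald test has no small-sample correction: with an unstructured covariance and a chi-square reference its size would be about 7–9%, not 5%, and the outcome scale is left open

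*SAP*

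**What the plan says.** SAP 4.1.1 makes arm A versus arm B the primary comparison. It uses response profiles if the pain trend is not linear, treats time as a factor (baseline and weeks 1, 3, 5, 7 and 8), and drops the group main effect by assuming equal baseline means.

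- Test: "The treatment effect over time will be assessed by the significance of the treatment arm x time interaction using Wald test".
- Covariance: "We will compare different covariance pattern models (e.g., unstructured, compound symmetry) based on AIC", with the best-fitting model then used.
- Outcome scale: "Data transformation (e.g., log10, square root) may be performed to improve distribution normality as appropriate".

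On error rates, SAP 5.1 states: "Power estimates for each outcome assumed a 5% significance level". SAP section 6 rules out an interim comparison of primary outcomes, unless the DSMC asks for one, so as to preserve power and "the overall Type I error at 0.05 level till the end of the study".

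The SAP does not say whether the Wald statistic is referred to chi-square or F, how denominator degrees of freedom are obtained, whether fitting is by ML or REML, which covariance structures beyond the two examples are candidates, or what would trigger a transformation. SAP 4.1.2 reuses the analysis for A versus C and B versus C. SAP 4.2.1 uses a similar one for the secondary outcomes measured at the six visits.

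**The concern.** Six time points give an unstructured covariance 6 × 7 / 2 = 21 parameters, estimated here from 66 to 120 participants. A Wald statistic referred to chi-square treats those estimates as known. With several degrees of freedom tested jointly, that makes the test reject too often, so the primary p-value could be too small while the SAP states a 5% level.

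The scale is a second open choice. With no trigger, and no statement that the decision is made blind to arm, the analyst could settle the scale of the primary effect after seeing the data. On a transformed scale the treatment effect is no longer in pain points.

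**Working it through.** **Inputs.** Arms of 40 randomized and 33 expected completers (SAP 2.2 and 5.1); six time levels and equal baseline means (SAP 4.1.1); 5% level (SAP 5.1). The documents give no covariance matrix, so those used in the simulations are assumptions.

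**The plan's own figure.** SAP 5.1 claims 80% power at d = 0.54 (33 per arm) and d = 0.58 (29 per arm). Take a two-sided linear-slope test on weeks 0, 1, 3, 5, 7, 8 (sum of squares 52), scaled to week 8 and standardised by the SD of change under exchangeable correlation:

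d = (1.960 + 0.842) × √[(2/n) × (64/52) / 2]

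- n = 33: d = 0.541; power at 0.54 is 79.8%.
- n = 29: d = 0.577; power at 0.58 is 80.4%.

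Both stated figures reproduce, but for a 1-df slope test. They say nothing about the size of the multi-df profile test.

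**Degrees of freedom.** Six time levels less the constrained baseline leave five A-versus-B differences, hence 5 df. This is inferred; the SAP does not state it.

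**Size with unstructured covariance and complete data.** For the corresponding baseline-adjusted comparison of the five follow-up means, the Wald statistic is a Hotelling T². With N participants and G arms in the model, ν = N − G − 1, and the 5% chi-square(5) critical value is 11.07:

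size (REML) = P{ F(5, ν − 4) > 11.07 (ν − 4) / (5ν) }

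ML multiplies the statistic by N/ν, so its threshold is 11.07 (ν − 4) / (5N).

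Example, two arms of 33: N = 66, ν = 63, threshold 11.07 × 59 / 315 = 2.07, and P{F(5, 59) > 2.07} = 8.2%.

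| Model | N | ν | REML | ML | F(5, ν) reference | 1-df, normal reference |
|---|---|---|---|---|---|---|
| 3 arms × 33 | 99 | 95 | 7.0% | 8.1% | 6.0% | 5.3% |
| 3 arms × 40 | 120 | 116 | 6.6% | 7.5% | 5.8% | 5.2% |
| 2 arms × 33 | 66 | 63 | 8.2% | 9.5% | 6.5% | 5.4% |
| 2 arms × 40 | 80 | 77 | 7.5% | 8.6% | 6.2% | 5.4% |

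The critical value that gives exactly 5% is 5ν/(ν − 4) × F₀.₉₅(5, ν − 4), which runs from 11.9 (N = 120) to 12.7 (N = 66).

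**Simulation of the baseline-constrained model under the null, unstructured, chi-square reference** (5,000–10,000 runs per setting). With 16% dropout, size was about 7.0–7.6% (three arms, REML), 8.3% (three arms, ML), 7.8–9.2% (two arms, REML) and 9.4–9.9% (two arms, ML). Two complete arms of 33 under REML gave 8.9–9.5%, somewhat above the 8.2% in the table. A three-arm test (10 df) gave about 7.5–9.7%.

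**What the AIC rule does.** This depends on the true covariance and the candidate list.

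| Assumed truth | Candidates | Unstructured chosen | Size |
|---|---|---|---|
| Compound symmetry | CS, unstructured | under 1% | 4.9–6.1% |
| Clear decay with time, or unequal variances | CS, unstructured | 74–100% | 6.7–9.9% |
| Mild decay (0.7 × 0.97 or 0.985 to the power of weeks apart) | CS, unstructured | 3–25% | 5.9–6.2% in three settings, 8.3% in one |
| Strong decay | equal-step AR(1) added | 32–77% | 6.7–7.9% |
| Strong decay | spatial-power structures added | about 1% | 5.0–6.1% |

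The last three rows rest on 1,000 runs per setting (Monte Carlo SE about 0.7–0.9 points).

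**The case against.** A reader might infer that the primary test simply has a size of 7–9%. The SAP does not support that. The figure needs unstructured to be chosen, an uncorrected chi-square reference, and the profile model, which is conditional on a non-linear trend. A Wald test can be reported with an F reference, and a Hotelling-type F would hold 5% on complete data. All of this stands, and the figure must be read as conditional.

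A reader might also infer that AIC will select unstructured whenever correlation fades with time. The simulations contradict this: under mild decay compound symmetry usually won, and with a well-fitting parsimonious structure on the list unstructured was rarely chosen and size stayed at 5–6%.

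Nor are the confidence intervals shown to be materially too narrow. They are 1-df quantities, and under unstructured covariance with a normal reference the exact size is 5.2–5.4%. The simulated 1-df average contrast ran at 4.4–6.0%, apart from 6.5–7.1% in two-arm fits under one assumed covariance. SAP 4.1.1's comparison of average change over weeks 5–8 is therefore much less exposed than the interaction test.

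On the transformation, the wording is permissive and no inflation has been shown. That log10 is undefined at zero matters little, because the outcome is a weekly or biweekly diary average and entry requires average pain above 3/10. What remains is the missing rule and the loss of pain-point units.

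None of this closes the gap. The routes that would hold the level are open choices in the SAP, and F with between-subject degrees of freedom, the simplest of them, still gives 5.8–6.5% under unstructured covariance.

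**Conclusion.** The concern holds in conditional form. An analyst who follows SAP 4.1.1, obtains unstructured from AIC and uses a chi-square Wald test will test the primary interaction at 6.6–8.2% (REML) or 7.5–9.5% (ML) for 33–40 per arm. These are exact complete-data values; simulated values for the constrained model are similar or somewhat higher. If compound symmetry holds, or a parsimonious structure that fits is selected, size is about 5–6%. This is more than missing detail, because one direct reading of the stated procedure gives a primary p-value that does not have the 5% level the SAP claims. The freedom to transform the outcome is a separate gap, supported by the text but not quantified.

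**What to change.** Amend SAP 4.1.1, before unblinding, as follows.

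1. Fit the primary model by REML. Use Kenward-Roger (or an equivalent small-sample) F tests for the interaction, and t tests and intervals for the contrasts.
2. Preferably fix unstructured covariance in advance, with a named fallback used only for non-convergence, in place of AIC selection. If AIC is kept, list every candidate structure and still use the small-sample tests.
3. Make the untransformed 0–10 score the primary outcome, with any log10 or square-root analysis as a sensitivity analysis.

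Carry the same wording into SAP 4.1.2 and 4.2.1. The cost is a few lines of text and a standard software option, with no new data or participants. The critical value rises slightly: on the complete-data calculation, from 11.07 to between 11.9 and 12.7 for the 5-df test.

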Both of the above studies were 6-hour human laboratory experiments. The present study is designed to evaluate whether or not the medium dose of cannabis (3.5%) can maintain an analgesic response over an eight-week period. In addition, a direct comparison of this vaporized preparation will be made with dronabinol and placebo. The medium dose of cannabis (3.5%) has been selected as it was utilized in a human experimental laboratory experiment that compared inhaled Δ9-THC and dronabinol.⁶ Using the cold-pressor test, participants immersed their hand in cold water (4 degrees C), and the time to report pain (pain sensitivity) and withdraw the hand from the water (pain tolerance) was recorded. Compared with placebo, marijuana and dronabinol decreased pain sensitivity, increased pain tolerance, and decreased subjective ratings of pain intensity. The magnitude of peak change in pain sensitivity and tolerance did not differ between marijuana and dronabinol, although dronabinol produced analgesia that was of a longer duration. Marijuana and dronabinol also increased abuse-related subjective ratings relative to placebo; these ratings were greater with marijuana. These data indicate that under controlled conditions, marijuana and dronabinol decreased pain, with dronabinol producing longer-lasting decreases in pain sensitivity and lower ratings of abuse-related subjective effects than marijuana.

A direct comparison of cannabis and dronabinol has not been performed in a clinical population. The present study will fill this void by performing a randomized, double-blind placebo controlled 8-week trial comparing the effectiveness of oral versus vaporized cannabis in patients with chronic low back pain. In addition to studying efficacy, we will also perform a driving simulation study to determine the real-world impact of cannabinoid treatments.

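### The primary arm-by-time test can be significant because of a difference confined to titration, and SAP 4.1.1 does not say whether it or the weeks 5–8 comparison decides

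*SAP*

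**What the plan says.** SAP 4.1.1 makes arm A versus arm B the primary comparison of diary pain intensity. The arm main effect is removed by assuming equal baseline means, and time is a factor with baseline and weeks 1, 3, 5, 7 and 8 as levels. The rule for the effect is: "The treatment effect over time will be assessed by the significance of the treatment arm x time interaction using Wald test". The next sentence, opening with the word *also*, compares average change from baseline over weeks 5–8. No order is set between the two, and nothing says what is concluded if they disagree.

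Earlier in the same section, response-profile analysis is tied to the trend over time not being linear. The sentence that makes time a factor does not repeat that condition.

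SAP 1 places titration in weeks 0–4 and treatment in weeks 5–8. Protocol section 9, Table 1, shows lower maximum amounts in weeks 1 and 3 than in weeks 4–8.

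SAP 5.1 sizes the trial on one time point: "This effect size is based on differences between groups of changes from baseline at the end of the study (week 8"). Protocol section 7 describes the study as designed to "evaluate whether or not the medium dose of cannabis (3.5%) can maintain an analgesic response over an eight-week period".

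**The concern.** With baseline means equal, the A versus B interaction null is that all five post-baseline differences are zero. Two of the five fall in titration. The test is unsigned and gives those two weeks the same standing as the rest. It can be significant because a difference is sustained, because it appears early and is lost, or because one product starts to work sooner.

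The last pattern is not far-fetched. SAP 4.3.2 itself expects dronabinol's effect to be delayed relative to whole-plant cannabis, without saying whether by hours or by weeks.

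At stake is what a positive primary result means. A report could claim a treatment effect from the interaction although the arms are equal throughout weeks 5–8, and the SAP has no rule against it. Two unranked analyses also give two routes to a positive finding.

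**Working it through.** **Inputs from the documents.** 33 per arm (SAP 5.1: "power was calculated for 33 subjects per treatment arm (total N=99) for Aims 1 and 2"); 5% level, taken as two-sided because the side is not stated; visits at weeks 0, 1, 3, 5, 7 and 8; equal baseline means (SAP 4.1.1).

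**Assumed, because the documents give no covariance.** Compound symmetry with correlation 0.5 or 0.7, or correlation decaying with time to 0.5 or 0.7 at four weeks. Differences are in SDs of the pain score at one time point unless stated otherwise.

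**Step 1: the plan's own figure.** SAP 5.1 states: "We have 80% power to detect effect sizes equivalent to Cohen's $d=0.54$ and $d=0.58$ for sample sizes 33 and 29 respectively". The slope-difference formula is m = 2(z_a+z_b)²σ²(1−ρ)/(SSx × slope²), with slope = d·σ√(2(1−ρ))/8. The visit times have mean 4, so SSx = 16+9+1+1+9+16 = 52. ρ cancels, leaving d = (1.960+0.842)×8/√(52m).
- m = 33: 22.41/√1716 = 0.541
- m = 29: 22.41/√1508 = 0.577

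Both match. The stated power is therefore for a 1-df linear slope. That is neither the 5-df test nor the weeks 5–8 contrast.

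**Step 2: the 5-df test against a titration-only difference.** The noncentrality is (n/2)·d′S⁻¹d, where S is the covariance of the five post-baseline means given baseline. Worked case, compound symmetry 0.5:
- S = 0.5I + 0.25J, so S⁻¹ = 2I − 0.2857J.
- For d = (0.5, 0.25, 0, 0, 0): d′S⁻¹d = 2(0.3125) − 0.2857(0.5625) = 0.464, and 16.5 × 0.464 = 7.66.
- On 5 df this rejects 54% of the time (chi-square), or 50% (F with 5 and 62 df).
- For (0.2, 0.1, 0, 0, 0) the noncentrality is 0.16 × 7.66 = 1.23, giving 11%.

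Rejection rates in %, chi-square/F (chi-square only in the 0.2, 0.1 column):

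| Assumed correlation | 0.5, 0.25 SD at weeks 1, 3 | 0.3, 0.3 SD | 0.2, 0.1 SD | Weeks 5–8 contrast |
|---|---|---|---|---|
| Compound symmetry 0.5 | 54/50 | 31/28 | 11 | 5 |
| Compound symmetry 0.7 | 78/74 | 49/45 | 16 | 5 |
| Decay to 0.5 | 88/84 | 49/45 | 19 | 5 |
| Decay to 0.7 | 99/99 | 79/75 | 34 | 5 |

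The last column is 5% by construction, since the true weeks 5–8 difference is zero.

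**Step 3: at the SAP's own effect size.** Here 0.54 is in SDs of change, under compound symmetry with correlation 0.8 down to 0.3.

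| True pattern | 5-df test | Weeks 5–8 contrast |
|---|---|---|
| 0.54 at weeks 1 and 3 only | 81–86% | 5% |
| 0.54 at week 1 alone or week 3 alone | 57–59% | 5% |
| 0.54 at weeks 5, 7 and 8 only | 87–93% | 83–97% |
| Linear growth to 0.54 at week 8 | 59–76% | 68–90% |

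In 10,000 simulated trials with estimated unstructured covariance (correlation 0.3–0.7) and the first pattern, the interaction was significant and the weeks 5–8 contrast was not in 77–82%.

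**Step 4: two unranked routes.** With no difference at any week and the covariance known, the chance that at least one of the two tests is significant at 5% is about 8.6%.

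**The case against.** Much of the case on the other side stands.

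- **The rates are not errors.** A reader might infer that 50–99% is a false-positive rate. It is not. The SAP's null covers all five weeks, a titration-only difference is a real difference between profiles, and rejecting is correct. No passage states a null limited to weeks 5–8.
- **The test does not pick up every difference.** A reader might infer that any difference at any week makes it significant. The documents do not support that: a 0.2 and 0.1 SD pattern is detected only 11–34% of the time.
- **The maintenance question is not about A versus B.** A reader might infer that the interaction contradicts the protocol's stated purpose. But section 7 asks about maintenance for the cannabis product and adds the comparison with dronabinol separately. Aim 1 asks only whether the active treatments differ, without a time window.
- **The weeks 5–8 comparison is already planned.** In the titration-only case it would show no difference 95% of the time, and comparing the mean profiles would show the timing. What remains is that it has no rank and there is no rule for disagreement.
- **The factor-time form may be conditional** on a non-linear trend. A linear model would not remove the problem: under compound symmetry, an unconstrained slope test rejects about 41% of the time for the 0.54 titration-only pattern, with the slope in the opposite direction.
- **The weeks 5–8 mean is not the week 8 effect.** With 0.5 SD at weeks 5 and 7 and zero at week 8, the contrast rejects 36–68% of the time. Week 8 therefore needs to be reported beside it.

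**Conclusion.** The point holds as one of interpretation and ranking. SAP 4.1.1 attaches the treatment effect to an omnibus test whose significance does not show a difference in weeks 5–8 or at week 8, and leaves the analysis that would show one without rank. A moderate titration-only difference (0.3 SD at both weeks, or 0.5 and 0.25 SD) is significant 28–99% of the time; a small one (0.2 and 0.1 SD), 11–34%. These figures rest on 33 per arm and on assumed correlations and patterns, none of which the documents supply. That the test includes the titration weeks and has no direction needs no such assumption, provided time is analysed as a factor. The change should be made, because it yields a signed answer for the treatment period and closes a second route to a positive result.

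**What to change.** In SAP 4.1.1:
- Name the signed A−B difference in mean change from baseline over weeks 5–8, with its 95% interval from the same model, as the single deciding primary test at 5%.
- Report the week 8 difference with its interval beside it.
- Report the arm-by-time interaction as supportive description of onset and durability, not as evidence of a treatment effect on its own.
- State whether time is a factor in all cases or only when the trend is not linear.

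In SAP 5.1, restate the power for the chosen contrast, with the assumed correlation.

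The cost is SAP wording and one power calculation; the model and the contrast are already planned. SAP 4.1.2 and 4.2.1 reuse the same strategy, so they should follow the change. There are two downsides. A difference confined to titration no longer counts as a positive primary result. And an A−B contrast does not by itself show that arm A's own response was maintained.
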